4. STUDY DESIGN AND METHODS

4.1 Recruitment of Subjects

Patients having either liver or pancreas cancer, who will be treated with radiation therapy will be invited to participate in the study during patient consult.

We will enroll up to five volunteers in the preliminary study to optimize the MR scanning protocols to be used in the patient study. We will place flyers to recruit healthy volunteers from Montefiore Medical Center or Albert Einstein College of Medicine. All eligible volunteers that can undergo CPAP and MRI scanning will be accepted into the volunteer study. No remuneration to volunteers will be offered and there are no potential benefits other than the Radiology read of the MRI for incidental findings. There are no risks to volunteers participating in the study related to radiation exposure because only MRI will be performed.

4.2 Registration Procedures

- Patients who agree to participate in the study and who provide written informed consent will be enrolled.
- Patients must meet all eligibility criteria listed in Section 3. The study coordinator will verify eligibility, assign a case number, and register the patient prior to study specific participation. The following information will be recorded:
 - Protocol number
 - Patient's initials
 - Patient's medical record number
 - Patient demographic data, including gender, birth date, and race.

4.3 Study Design

4.3.1 A Volunteer Study to Optimize MRI Scanning Protocols with and without CPAP

Prior to enrolling patients in the study, a volunteer study will be conducted to optimize MRI scanning protocols with and without CPAP. The purpose of the volunteer study is to gain experience in using CPAP, to investigate appropriate MR imaging protocols with sufficient image resolution and contrast, and to test and streamline the workflow to minimize possible patient discomfort. Volunteers will not receive any MR contrast as part of their MR imaging and will be imaged two times once without the use of CPAP and once using CPAP employing the following

MR sequences: T1-weighted, T2-weighted, Dixon fat/water, ultra-short TE and other clinical or research MR sequences.

4.3.2 Image Acquisitions: CT, MRI, CBCT and orthogonal kV/MV images

We are planning to enroll a maximum of 42 patients into this study. Prior to abdominal radiotherapy, all eligible participants will undergo both CT and MRI scans in the radiotherapy treatment position. Two scanning protocols (Arm 1 and Arm 2) will be performed according to their CPAP eligibility.

- (1) Arm 1: For patients not eligible for CPAP or unable to tolerate CPAP
 - Breath-hold CT and 4D-CT without CPAP
 - Breath-hold MRI and 4D-MRI without CPAP
 - T1-weighted, T2-weighted, Dixon fat/water, and ultra-short TE images
- (2) Arm 2: For patients eligible for CPAP and able to tolerate CPAP
 - Breath-hold CT without CPAP
 - 4D-CT with and without CPAP
 - 4D-MRI with CPAP
 - T1-weighted, T2-weighted, Dixon fat/water, and ultra-short TE images

CT scans will be performed in the axial scanning mode with ~2 mm slice thickness over the entire abdomen region for treatment planning and dose calculations.

MRI images using standard clinical imaging sequences will be acquired, including T1-weighted, T2-weighted, and Dixon fat and water images. Additional MRI scans, such as ultrashort-TE (UTE) images, will follow MRI safety guideline of FDA and will be optimized based on phantom and volunteer studies before clinical studies. Gadolinium-based contrast may be administered per institutional routine and research protocol. The MRI scanning sequences for these MRI images will be optimized to achieve optimal resolution (~ 2 mm) and contrast with minimized geometric distortion (< 2 mm). MR images will be used (1) to delineate the targets following the standard treatment planning process, and (2) to create pseudo-CT for dose calculations and to be compared with CT-based dose calculations.

Patients will receive standard radiotherapy to liver or pancreatic lesions using 3D-conformal or IMRT techniques (using CT-based planning without CPAP motion management). Prior to each treatment delivery, patients will undergo kV/MV orthogonal images and CBCT scans, and the CBCT scans will be compared with the planned CT to verify treatment position. In off-line, the CBCT scans and kV/MV orthogonal images will be compared with pseudo-CT and DRRs that are created from pseudo-CT.

4.3.3 CPAP Procedures for Eligible Patients Enrolled in Arm 2

Before simulation and image acquisition with CPAP, patients will be fitted with a mask by a respiratory therapist and then undergo training on use of the CPAP device. Under physician supervision, patients will be instructed how to gradually increase air pressure from 5 cm H₂O to the maximal comfortably tolerated level up to a maximum of 15 cm H₂O. Patients were connected to CPAP for at least half an hour before undergoing image acquisition.

If CT and MRI scans could not be performed at the same day, patients will be discharged home with their mask, hose, and filter and be asked to bring them for next image acquisition. Detailed procedures are described as below,

- (1) Place patient in a sitting position
- (2) Assess vital signs every 15 minutes in the first hour and then every half an hour while on CPAP and monitor SpO₂ continuously

- (3) If systolic BP <90 mmHg contact Medical Control prior to beginning CPAP to assess patient stability
- (4) Begin at lowest level of positive pressure available
- (5) Explain the procedure to the patient:
- (6) Patient requires reassurance to be used effectively.
 - a. Example: "You are going to feel some pressure from the mask"
- (7) Place delivery device over mouth and/or nose. (depend on the type of mask is used)
Instruct patient to breath in through their nose slowly and exhale through their mouth as long as possible (count slowly and aloud to four then instruct to inhale slowly).
- (8) Check for air leaks
- (9) Documentation on the patient care record should include:
 - a. CPAP level
 - b. Frequent SpO₂ and Vital Sign assessment
 - c. Any adverse reactions

4.3.4 Methodology Development to Create Pseudo-CT from MRI and Its Evaluation

A method of using probabilistic classification of MRI to generate pseudo-CT has shown promising results in brain radiation therapy [11,19]. The probabilistic classification accounts for individual differences and the mixing of tissue types within voxel that result in the generated pseudo-CT close to true individual anatomy. We will first explore the potential of using this classification method to generate pseudo-CT in the abdomen, and then may explore a hybrid method (a combination of atlas- and voxel- based methods) to improve the quality of pseudo-CT. Probabilistic tissue classification is achieved via fuzzy c-means (FCM) clustering with a spatial constraint [11]. The FCM algorithm assigns voxels of the images a probability of belonging to a class. Membership probability in any given tissue class varies between zero and one. The membership for each voxel can be obtained by minimizing the objective function. Then relative attenuation properties are assigned based on the probability map and pseudo-CT is generated.

To evaluate the quality of pseudo-CT in treatment planning, 3D-conformal and IMRT plans will be created on standard CT and then the plans will be mapped onto pseudo-CT. Dose distributions and dose volume histograms will be compared between the plans using CT and pseudo-CT datasets.

To evaluate the quality of pseudo-CT in image guidance using bony structure, DRRs generated from pseudo-CT and CT will be both aligned to the orthogonal images that are taken prior to treatment. To evaluate the quality of pseudo-CT in image guidance using soft tissue, pseudo-CT and CT will be both aligned to CBCT that are taken prior to treatment. The accuracy of image alignment using pseudo-CT will be evaluated.

4.3.5 Methodology Development to Create Pseudo-MRI from CBCT and Its Evaluation

CBCT has a limitation in differentiating targets from normal tissues. To better visualize targets and soft tissues, the method to synthesize MRI will be explored. The proposed method will use planning MRI images and their associated pseudo-CT images as well as CBCT images. First, CBCT is registered to pseudo-CT using rigid or deformable registration. Second, the transformation information from the previous registration is applied to the planning MRI to generate a synthetic CBCT-based MRI for target localization and alignment during treatment. To evaluate the quality of pseudo-MRI in target localization and alignment, the alignment using pseudo-MRI and planning CT will be compared with the alignment using CBCT and planning CT.

4.3.6 Study of the Potential Role of 4D-MRI in Treatment Planning and Image Guidance

4D-CT is usually acquired for motion assessment and management when treating tumors in chest and abdomen. When contouring target volumes, internal target volume (ITV) is defined based on the 4D-CT dataset in order to account for target motion. For abdominal tumors, it is challenging to directly assess target motion on 4D-CT without contrast administration or implantation of fiducial

markers. Thus, replacement of 4D-CT with 4D-MRI would be a beneficial step for motion assessment and an important part in the MRI-alone workflow for abdominal radiotherapy. To investigate the role of 4D-MRI in treatment planning, ITVs contoured using 4D-CT and 4D-MRI will be compared, and their dosimetric impact will be also evaluated.

4.3.7 CPAP Effect on Motion Reduction and Clinical Treatment Outcome

CT images will be acquired without and with CPAP for patients enrolled in Arm 2. Following routine contouring and planning procedures for abdominal treatment, gross tumor volume (GTV) and clinical target volume (CTV), ITV to account for tumor motion, and planning target volume (PTV) to account for setup errors will be identified and contoured on each CT dataset. Treatment plans will be generated on both CT datasets with their corresponding target contours using the same plan objectives.

To evaluate motion reduction using CPAP, tumor excursion (in superior-inferior, right-left and anterior-posterior directions) and ITV will be calculated and compared between two datasets for Arm 2 participants. To evaluate the change on clinical outcome, dose metrics such as mean dose to critical organs and complication rates will be compared.

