1. PROTOCOL SUMMARY AND/OR SCHEMA

- **Specific Objectives**

- To explore the feasibility of using Magnetic Resonance Imaging (MRI) alone in abdominal radiation therapy for treatment planning and target localization
- To demonstrate continuous positive airway pressure (CPAP) in motion reduction for abdominal radiation therapy

- **Eligibility**

- Patients who have liver or pancreas tumors and will be treated with radiation therapy
- Patients who are able to commit to Magnetic Resonance Imaging (MRI)

[figure not shown]
- **Required Sample Size**

- A maximum of 47 subjects (42 patients + 5 healthy volunteers) over a 24-month period

- **Study Design and Methods**

- All patients participating in the study will receive standard radiation therapy.
- Source of data for the study include CT, MRI, cone beam-CT (CBCT) and orthogonal kV/MV images and treatment plans.
- Patients will undergo both CT and MRI prior to abdominal radiation therapy and CBCT and orthogonal kV/MV images prior to each treatment delivery.
- A two arm study will be performed and patients will be enrolled into a given arm according to their eligibility. Arm 1 is for patients that are either not eligible for CPAP or that are unable to tolerate CPAP. These patients will undergo breath-hold and 4D imaging for both CT and MRI without CPAP. Arm 2 is for patients that are eligible for CPAP and able to tolerate CPAP. These patients will undergo breath-hold CT without CPAP, 4D-CT with and without CPAP and 4D-MRI with CPAP.
- Two specific aims will be investigated. In Aim 1, we will explore the feasibility of using a MRI-only in Radiation Oncology workflow. A probabilistic classification method will be utilized to generate a pseudo-CT from MRI to support treatment planning and image guidance for radiation therapy. The quality of the pseudo-CT will be evaluated by comparing it with CT. In addition, the reverse mapping will be investigated to create pseudo-MRI from CBCT to improve visualization of treatment targets and soft tissue prior to treatment delivery. In Aim 2, we will evaluate the utility of CPAP as a novel motion reduction methodology for patients with liver and pancreas cancer, to this end CT images with and without CPAP will be used. The evaluation will be based on the changes of motion magnitude, the achievable volumetric reduction in treatment target volumes, and doses to the targets and critical organs.

- **Schema**

Sample size: a maximum of 42 patients

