3. INCLUSION/EXCLUSION CRITERIA

3.1 Selection of Patient Subjects at the Albert Einstein College of Medicine/Montefiore Medical Center

To study the feasibility of a MRI-only workflow with/or without CPAP in abdominal radiation therapy, the following patients will be **included**:

- Eligibility Criteria
 - Patients have liver or pancreas tumors (either primary tumors or metastases) and are scheduled to be treated with radiotherapy (either 3D conformal or intensity-modulation radiotherapy (IMRT) with conventional or hypo-fractionation).
 - b. KPS ≥ 70
 - c. If a biopsy is performed, the patient is at least 1 week post-biopsy.
 - d. The patient's age must exceed 18 years.
 - e. The patients must be able to commit to T1-weighted, T2-weighted, Dixon fat and water, ultrashort-TE, and other clinical or research MR sequence images prior to treatment.
 - f. CPAP Eligibility: CPAP is a safe, effective form of therapy with rare complications. Relative contraindications include patients with bullous lung disease, fibrotic lung disease, Claustrophobia and recurrent sinus or ear infections. The absolute contraindications include obtundation /unconsciousness, chest wall trauma, suspected pneumothorax, persistent nausea/vomiting, active upper GI bleeding, history of recent gastric surgery, facial anomalies/trauma [15,16]. If there is any question about the above history and medical problems, the subject will be referred to a pulmonologist for consultation.
 - i. The patients with above contraindications are not CPAP eligible and are enrolled in Arm 1 for the protocol without CPAP
 - ii. The eligible patients are enrolled in Arm 2 for the protocol with CPAP.

Exclusion Criteria:

- Patients who meet the following criteria:
 - a. Any medical condition, which would make the imaging studies unsafe or poorly tolerated
 - b. Known allergic reaction to contrast or shellfish
 - c. Implanted metal devices or foreign bodies that serve as a contraindication to MR imaging
 - d. Creatinine > 1.4 mg/dl and Creatinine clearance < 20 mg/dl.
 - e. Uncontrolled, clinically significant cardiac arrhythmias
 - f. Severe claustrophobia
 - g. Pregnant female
 - h. KPS < 70

3.2 Selection of Healthy Volunteers at the Albert Einstein College of Medicine/Montefiore Medical Center

To optimize the MRI scanning protocols with and without CPAP volunteers that meet the following eligibility criteria will be **included**:

Eligibility Criteria

- a. KPS ≥ 70

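### Section 4.3.7 presents a comparison of treatment plans as CPAP's effect on clinical outcome, but no patient is treated on a with-CPAP plan, so it can show only a predicted dosimetric effect

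*Combined protocol and SAP*

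**What the plan says.** Section 4.3.7 describes two CT datasets per Arm 2 patient, one without and one with CPAP. It then states: "Treatment plans will be generated on both CT datasets with their corresponding target contours using the same plan objectives". Motion is judged by tumor excursion and ITV. The last sentence reads: "To evaluate the change on clinical outcome, dose metrics such as mean dose to critical organs and complication rates will be compared". The section heading pairs motion reduction with *Clinical Treatment Outcome*.

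On treatment, section 1 says: "All patients participating in the study will receive standard radiation therapy". Section 4.3.2 adds that this is done "using CT-based planning without CPAP motion management", with no exception for Arm 2.

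On the use of CPAP, section 4.3.3 says: "Before simulation and image acquisition with CPAP, patients will be fitted with a mask by a respiratory therapist and then undergo training". If CT and MRI fall on different days, patients are "discharged home with their mask, hose, and filter and be asked to bring them for next image acquisition". No section provides for CPAP during treatment delivery or for delivering a with-CPAP plan.

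On arm assignment, section 1 says: "Arm 1 is for patients that are either not eligible for CPAP or that are unable to tolerate CPAP". Section 3.1 says: "The patients with above contraindications are not CPAP eligible and are enrolled in Arm 1 for the protocol without CPAP".

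**The concern.** A change in clinical outcome due to CPAP can be observed only if some patients are treated with CPAP, or on a plan made with it. Here CPAP stops at imaging. The with-CPAP plan is generated and compared but not delivered, so section 4.3.7 attaches an outcome label to a planning comparison.

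The label matters because other sections point the same way. Section 2.1.2 gives reduced injury to normal tissue as a goal of CPAP and links it to accuracy during radiation delivery, a step at which this trial does not use CPAP. The second primary hypothesis in section 2.2 also mentions minimizing injury. A report that followed the heading and last sentence of 4.3.7 literally could present plan-based predictions as evidence of clinical benefit.

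**Working it through.** **1. The plan's own figure.** The only CPAP endpoint with a power statement is motion reduction (section 5.2): mean difference 12%, SD 13%, 21 patients, two-sided paired t-test, α = 0.01, stated power 90%.

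- Noncentrality = (12/13) × √21 = 0.923 × 4.583 = 4.23, with 21 − 1 = 20 degrees of freedom.
- Power from the noncentral t distribution = 90.2%, which reproduces the stated 90%.

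The sample size is therefore not in question. It was not derived for any dose or complication measure.

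**2. Patients treated on a with-CPAP plan.** Section 5.2 gives a maximum of 42 patients, with the CPAP arm closed at 21. Sections 1 and 4.3.2 have all of them treated without CPAP motion management.

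- Overall: 42 − 42 = 0.
- Arm 2: 21 − 21 = 0.

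**3. What each possible comparison could show.**

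| Comparison | Data the design provides | What it can show about CPAP |
|---|---|---|
| Observed complications, treated with versus without CPAP | None on the with-CPAP side | Nothing |
| Observed complications, Arm 2 versus Arm 1 | Both arms treated without CPAP; arm follows eligibility and tolerance | Nothing; a difference would not be a CPAP treatment effect |
| Dose or complication probability calculated from the paired plans | Up to 21 pairs in Arm 2 | A predicted dosimetric effect |

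Only the third row is informative, and it is not an observed clinical outcome.

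**4. Section 4.3.7 against the stated aim.** Section 1 bases the CPAP evaluation on motion magnitude, reduction in target volumes, and doses to targets and critical organs. Specific Aim 2 in section 2.3 lists pseudo-CT image quality, target delineation, tumor motion and critical-organ dose. Neither lists complications or clinical outcome, so section 4.3.7 goes beyond both.

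**5. What is specified for complication rates.** The documents give no definition of a complication for this comparison, no follow-up schedule for one, and no prediction model, parameters or organs. Appendix I covers adverse event reporting for safety, but nothing links it to section 4.3.7.

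**The case against.** The strongest reply is that the sentence lists complication rates as a dose metric, directly after describing two plans per Arm 2 patient made with the same objectives. Sections 4.3.4 and 4.3.6 also compare doses across image datasets. With no follow-up or complication endpoint described, rates calculated from the plans are the natural meaning, and such a comparison is valid. That stands. What remains is that the text does not say the rates are predicted, names no model, and calls the result a change in clinical outcome.

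A second reply is that sections 1 and 2.3 already confine Aim 2 to motion, volume, dose and image quality, and that only motion is powered. This also stands, and it limits the consequence. It does not remove the inconsistency, because the heading and sentence remain and section 2.2 mentions injury.

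A reader might infer something stronger: that the trial plans to compare observed complications, perhaps between arms, and would attribute the difference to CPAP. The documents do not support this. No such analysis is proposed, and the wording points to the paired plans. Nor do they support deleting the complication measure outright, since a plan-derived version may be intended and can be valid.

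**Conclusion.** The point holds as a mismatch between what section 4.3.7 claims and what the design can show. Its size is a count: 0 of up to 21 Arm 2 patients are treated on a with-CPAP plan, while up to 21 pairs of plans can be compared. The comparison can support a statement about predicted dose and, if a model is fixed, predicted complication probability. It cannot support a statement about clinical outcome.

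This rests on two readings: that the treatment statement in section 4.3.2 applies to both arms, since no exception is given, and that CPAP is confined to training and imaging, as section 4.3.3 describes.

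The correction is worth making but does not threaten the trial. The measure is secondary and unpowered. The motion, ITV and mean-dose comparisons and the stated power are unaffected. It would be wrong to infer that the paired dose comparison is invalid, or that a misleading conclusion is certain; the aims in sections 1 and 2.3 are already narrower. How patients should be treated is not at issue.

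**What to change.** In the heading of section 4.3.7, replace *Clinical Treatment Outcome* with *Predicted Dosimetric Effect*. Replace the last sentence with text such as:

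> To assess the predicted dosimetric effect of CPAP, plan dose metrics (for example, mean critical-organ dose) and, if retained, predicted normal tissue complication probability (model, parameters and organs fixed before calculation) will be compared between the paired with-CPAP and without-CPAP plans of Arm 2 patients. No conclusion on observed clinical outcome will be drawn.

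This brings section 4.3.7 into line with sections 1, 2.3 and 4.3.2, and keeps a plan-derived complication measure if the sponsor intended one. It needs no new images, plans or patients. The costs are a narrower claim and, if the probability is kept, the work of specifying its model in advance.

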4.4 Clinical MRI Assessment

All images will be reviewed by a board certified radiologist to assess for unexpected findings. In case of unexpected clinically relevant imaging findings the Study-PI, [name], will inform study participants of these findings.

5 STATISTICAL CONSIDERATIONS

5.1 Statistical Considerations for Specific Aim 1

The primary clinical end point of specific aim 1 is to show the non-inferiority of the 4D-MR only workflow for ITV definition to that using 4D-CT. In the case of lung cancer Ehler et al. [20] have found using 4D-CT that different methodologies for the definition of the ITV yielded differences in ITV definition ranging from 1.7% to 43% with an average difference between methodologies of 17.5%. The observed differences in volume definition were confined to the periphery of the ITV volume. Therefore a difference of no larger than 14% between the ITV defined using our proposed 4D MR workflow versus 4D CT is considered as not being clinically meaningful. Based on the literature assuming a standard deviation of 16.3% and a non-inferiority margin of 14% in ITV volume definition between 4D-MR and 4D-CT, we find that if there is truly no difference between the ITV definition using 4D-CT and the ITV definition using 4D-MR. A sample size of 21 patients will achieve a 91% power to detect the non-inferiority using a one sided t-test and the true difference between the mean is 0. at a type 1 error rate of 0.01.

5.2 Statistical Considerations for Specific Aim 2

Using a conventional motion reduction technique employing an abdominal compression pillow we have found an average motion reduction of 12% with a standard deviation of 13% for lesions within the lung [21]. Achievable motion reduction ranged from 3% to 28%, therefore an average motion reduction of at least 12% with CPAP is considered clinically meaningful. Using pairwise analysis assuming a mean difference of 12% between free breathing and the application of CPAP with an associated standard deviation of 13%, and an $\alpha=0.01$, using a two sided paired t-test we find that with 21 patients will have 90% power to detect a motion reduction of at least 12% when using CPAP. Assuming an allocation ratio of 1:1 between the two arms of this study we are planning to recruit a maximum of 42 patients to this study, however once, 21 patients have been

accrued to the CPAP arm no further patients will be enrolled into that part of the study and the study will be closed once the necessary patient number for aim 1 has been achieved.

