2.3 Aims

Specific Aim 1: (1) Investigate methods to generate pseudo-CT to support radiotherapy treatment planning and image guidance for abdominal treatments. (2) Explore the feasibility to map CBCT to MRI intensities for improving the visualization of tumors and/or soft tissues for on-line treatment verification using CBCT-based methods. (3) Evaluate the potential role of 4D MRI and their associated pseudo-CT in target delineation for treatment planning and target localization for image guidance.

Specific Aim 2: Determine the effect of CPAP on pseudo-CT image quality, target delineation, tumor motion and dose to critical organs in abdominal radiotherapy.

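### Aim 1 claims non-inferiority for ITV definition, but its test covers only the signed mean difference in ITV volume

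*Combined protocol and SAP*

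**What the plan says.** Section 5.1 gives the primary end point of Aim 1 as "to show the non-inferiority of the 4D-MR only workflow for ITV definition to that using 4D-CT". It argues the limit from a cited lung study using 4D-CT, in which ITV methods differed by 1.7% to 43% (average 17.5%), and adds: "The observed differences in volume definition were confined to the periphery of the ITV volume". It then concludes: "Therefore a difference of no larger than 14% between the ITV defined using our proposed 4D MR workflow versus 4D CT is considered as not" clinically meaningful.

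The sample size follows by "assuming a standard deviation of 16.3% and a non-inferiority margin of 14% in ITV volume definition between 4D-MR and 4D-CT", "using a one sided t-test and the true difference between the mean is 0" and "at a type 1 error rate of 0.01", which is said to give 91% power with 21 patients.

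Two other places bear on the point. Section 2.3 includes in Aim 1: "Evaluate the potential role of 4D MRI and their associated pseudo-CT in target delineation for treatment planning and target localization for image guidance". Section 4.3.6 says "ITVs contoured using 4D-CT and 4D-MRI will be compared, and their dosimetric impact will be also evaluated", but names no measure, no threshold and no link to the test in section 5.1.

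**The concern.** The claim is wider than the parameter. An ITV says where to treat as well as how much, and the tested quantity is a percentage difference in volume. Two ITVs of equal size in different places score 0%. A signed mean also lets an ITV that is 20% too large in one patient offset one that is 20% too small in another.

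The argument for 14% includes a remark about where the differences lay in the cited study. Nothing in the plan checks whether the same is true between 4D-MR and 4D-CT in the abdomen, where section 2.1 expects registration uncertainty to be larger than at other sites.

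At stake is the wording of the Aim 1 conclusion. A passed test could be reported as showing that 4D-MR is non-inferior for defining ITVs, when it shows only that the average volume is similar.

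**Working it through.** **Inputs from section 5.1:** margin 14%, SD 16.3%, n = 21, one-sided alpha 0.01, true mean difference 0, stated power 91%. Normality of the patient differences is my assumption.

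**1. Reproduce the stated power.** For a paired (one-sample) one-sided t-test:
- noncentrality = (14 / 16.3) × √21 = 3.94, with 20 degrees of freedom
- critical t = 2.528
- power from the noncentral t = 0.909, which matches 91%

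Two independent groups of 21 would give 0.641, so the plan's figure is for a paired analysis.

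**2. The differences are signed.** A true mean of 0 with an SD of 16.3% is impossible for absolute differences, because their mean is 0 only if every difference is 0. The design therefore lets positive and negative differences cancel.

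**3. Patients beyond 14% under the same assumptions.**
- 14 / 16.3 = 0.859 SD
- P(difference > +14%) = P(difference < −14%) = 0.195, about 4 of 21 on each side
- P(|difference| > 14%) = 0.390, or 0.390 × 21 = 8.2 patients
- 95% limits of agreement = ±1.96 × 16.3% = about ±32%

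**4. What passes.** At the assumed SD, the observed mean in the tested direction may be as large as 14 − 2.528 × 16.3 / √21 = 14 − 9.0 = 5.0%.

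**5. Position (illustration only).** The documents give no ITV sizes or expected shifts, so the following are assumptions. For two spheres of equal radius r with centres d apart, the shared fraction is 1 − 3d/(4r) + d³/(16r³). The volume difference is 0% in every row.

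| ITV diameter | Shift | Shared fraction | Part of the 4D-CT ITV outside the 4D-MR ITV |
|---|---|---|---|
| 30 mm | 3 mm | 0.850 | 15% |
| 30 mm | 5 mm | 0.752 | 25% |
| 50 mm | 3 mm | 0.910 | 9% |
| 50 mm | 5 mm | 0.850 | 15% |

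**6. Whether another section closes the gap.** Section 4.3.6 plans an ITV comparison and a dosimetric evaluation. Sections 4.3.4 and 4.3.5 plan alignment checks for pseudo-CT and pseudo-MRI. None gives an acceptance limit, and none enters the non-inferiority decision.

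**The case against.** The strongest reply is that volume is not the only thing the trial will look at. The dosimetric comparison in section 4.3.6 could reveal a displaced ITV, and localization has its own evaluations in sections 4.3.4 and 4.3.5. This stands: it would be wrong to infer that the plan assesses ITVs by volume alone. What remains is that these evaluations have no criterion and cannot alter the result of the test.

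Second, 14% is used as a margin for a mean, not as a limit for each patient, and any test of a mean leaves individual scatter. The cited CT methods themselves differed by up to 43%. This also stands. The 39% is therefore not evidence that 4D-MR is worse than 4D-CT; it shows how little the mean says about individual ITVs.

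Third, a reader might infer that the trial could approve ITVs that miss tumor. The documents do not support that. Non-overlap here means non-overlap with the 4D-CT ITV, and section 4.3.6 says target motion is hard to assess on 4D-CT without contrast or fiducials. The disagreement could lie on either side. Nor does section 5.1 say that the differences in the cited study were concentric; it says only that they were peripheral.

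Fourth, a spatial measure needs CT-MR registration, and section 2.1 treats that step as a source of error. A sound 4D-MR ITV could score poorly for that reason, whereas volume does not depend on registration. This is a good argument against making success depend on a spatial measure, but not against reporting one.

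**Conclusion.** The point holds as a mismatch between claim and parameter. The arithmetic in section 5.1 is correct. As written, however, the rule supports a conclusion about mean ITV volume and is labelled as one about ITV definition. On the design's own mean and SD, and assuming normality, about 39% of patients differ by more than 14% while the test passes 91% of the time. A purely positional disagreement contributes nothing to the test, whatever its size. The sphere figures only illustrate this and rest on assumed sizes and shifts.

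A reader might also infer a risk to participants. Section 4.3.2 rules that out for this trial, because treatment follows CT-based planning. The consequence is an overbroad conclusion from a feasibility study, so this is a cheap improvement and not an essential correction.

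**What to change.** In section 5.1, keep the t-test and restrict its conclusion to mean ITV volume. Prespecify these secondary analyses on the ITVs that section 4.3.6 already has contoured:

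- **Volume:** 95% limits of agreement for the percentage difference, and the proportion of patients within ±14%.
- **Space, per patient:** the fraction of the 4D-CT ITV covered by the 4D-MR ITV (or Dice), plus centroid shift or surface distance in mm.

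State that the spatial results include CT-MR registration error and use an imperfect reference, and that any wider claim about ITV definition must rest on them together with the volume test.

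The spatial measure need not be co-primary. That would require a threshold and an SD that the documents do not give, and the power at n = 21 would be unknown. Replacing the signed mean with a mean absolute difference is not a simple alternative either. Under the same assumptions that mean is 16.3 × √(2/π) = 13.0%, and showing it to be below 14% with 21 patients has only about 6% power (by simulation).

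The cost is some SAP wording, a defined registration step (the plan does not say that the two ITVs will be registered), modest extra analysis and a narrower headline claim. No new scans or patients are needed.
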